7.5.3. Subject Perception of Treatment

The following contingency table will be prepared to evaluate the subjects' perception of treatment received at Day 1 and at Week 24.

Assignment	Guess				Total
	SM04690 (1)	Vehicle (2)	Sham (3)	Don't Know (4)	
SM04690 (1)	$n_{11} (P_{1 1})$	$n_{12} (P_{2 1})$	$n_{13} (P_{3 1})$	$n_{14} (P_{4 1})$	$n_{1.}$
Vehicle (2)	$n_{21} (P_{1 2})$	$n_{22} (P_{2 2})$	$n_{23} (P_{3 2})$	$n_{24} (P_{4 2})$	$n_{2.}$
Sham (3)	$n_{31} (P_{1 3})$	$n_{32} (P_{2 3})$	$n_{33} (P_{3 3})$	$n_{34} (P_{4 3})$	$n_{3.}$
Total	$n_{.1}$	$n_{.2}$	$n_{.3}$	$n_{.4}$	N

$P_{ji} = P(\text{guess } j | \text{assigned treatment } i) = \text{probability of guessing treatment } j \text{ when assigned treatment } i$

Bang's Blinding Index (BI) (Bang et al. 2010) will be calculated to determine the percentage of unblinding that is beyond chance.

$$\text{Bang's BI}_i = \left(2 \frac{n_{ii}}{n_{i1} + n_{i2} + n_{i3}} - 1 \right) \times \left(\frac{n_{i1} + n_{i2} + n_{i3}}{n_{i1} + n_{i2} + n_{i3} + n_{i4}} \right),$$

where $\text{BI}_i = 0$ represents random guessing; $\text{BI}_i = 1$ represents complete unblinding;
 $\text{BI}_i = -1$ represents opposite guessing

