The Investigator completing the Physician Global Assessment must sign/initial and date the source document to indicate that the assessment is reported accurately. A study staff member will record the Physician Global Assessment score in the eCRF. The score is determined by measuring the distance (mm) between the “Very Good” anchor and the Investigator’s mark, providing a range of scores from 0 to 100.

The Physician Global Assessment of Disease Activity questionnaires will be provided by the Sponsor and may not be reproduced.

Evaluation of Success of Blinding

At Day 1 (post intra-articular injection) and Week 24 (EOS)/ET, subjects will complete a questionnaire on paper as to which treatment arm of the study they believe they were assigned to in order to evaluate the effectiveness of blinding. The questionnaire will capture responses of “Study drug injection,” “Injection of 2 mL inactive vehicle substance,” “Needle insertion into the knee with no vehicle substance injected,” and “Do not know.”

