10.4.7 EXPLORATORY ANALYSES

Change from baseline will be summarized with descriptive statistics at Weeks 4, 8, 12, 16, and 20 for WOMAC pain subscore, WOMAC function subscore, and Patient Global Assessment; at Weeks 4, 8, 12, 16, 20, and 24 for WOMAC total score, and KOOS (five subscales [Pain, Symptoms, ADL, Sport/Rec and QOL] as well as aggregate scores KOOS₄ and KOOS₅); and at Weeks 4, 12, and 24 for Physician Global Assessment. Change from baseline will also be statistically described for weekly KOOS-PS and weekly averages of daily pain NRS (aside from Week 24). Change over time in weekly NSAID usage will also be assessed at every week.

ANCOVA will be used to estimate the least squares difference in the change from baseline in exploratory outcomes between each of the four active treatment groups and the vehicle group, adjusted for baseline value. Additionally, ANCOVA will be used to estimate the least squares difference in the change from baseline in all outcomes (including primary and secondary) between the vehicle group and the sham group, adjusted for baseline value. Unadjusted 95% confidence intervals and P values will be reported.

MCP-Mod will estimate SM04690 dose response compared to vehicle using the results of the exploratory efficacy endpoint analyses.

As the study is stratified based upon known clinical phenotypes of OA, all exploratory efficacy analyses will be completed in three subject populations: 1) subjects with unilateral symptomatic OA, 2) subjects with unilateral symptomatic OA and without widespread pain ($WPI \leq 4$ and $SSQ2 \leq 2$), and 3) all subjects.

Evaluation of subject awareness of randomized treatment given and the success of blinding in this trial will be estimated using an appropriate categorical analysis. Specifically, the percentage of subjects accurately identifying the assigned treatment group will be estimated.

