10.5 SAMPLE SIZE

A sample size of approximately 630 subjects will be randomized at a ratio of 1:1:1:1:1:1 (0.03 mg active per 2 mL injection : 0.07 mg active per 2 mL injection : 0.15 mg active per 2 mL injection : 0.23 mg active per 2 mL injection : 0.0 mL vehicle : 2.0 mL vehicle). The sample size for this study was based upon accepted dose finding statistical practice (Ting et al. 2017).

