10.6.2 EVALUATION OF SUCCESS OF BLINDING

Subjects will be queried regarding the perceived effectiveness of blinding. Details of this analysis will be provided in the SAP.

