4.3. Exploratory Endpoints

Additional exploratory endpoints of this study include:

1. Evaluate change from baseline OA pain in the target knee as assessed by WOMAC Pain at Weeks 4, 8, 12, 16, and 20
2. Evaluate change from baseline OA function in the target knee as assessed by WOMAC Function at Weeks 4, 8, 12, 16, and 20
3. Evaluate change from baseline symptoms of OA in the target knee as assessed by WOMAC Total at Weeks 4, 8, 12, 16, 20, and 24
4. Evaluate change from baseline OA pain in the target knee at each week (aside from Week 24) as assessed by Pain NRS
5. Evaluate change from baseline OA disease activity as assessed by PTGA at Weeks 4, 8, 12, 16, and 20
6. Evaluate change from baseline OA function in the target knee as assessed by Knee Injury and Osteoarthritis Outcome Score (KOOS) at Weeks 4, 8, 12, 16, 20, and 24
7. Evaluate change from baseline OA function in the target knee at each week as assessed by KOOS Physical Function Short Form (KOOS-PS)
8. Evaluate change from baseline OA disease activity as assessed by Physician Global Assessment (PGA) at Weeks 4, 12, and 24
9. Evaluate change over time in NSAID usage as assessed by electronic diary responses at every week
10. Evaluate subject perception of study treatment received at Day 1 and Week 24
11. Evaluate outcome differences between treatment with sham and vehicle injections at Weeks 4, 8, 12, 16, 20 and 24

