5.2.8. Evaluation of Success of Blinding

Subjects were prompted, “Please indicate which treatment arm you believe you were assigned to for this study” on a paper form on Day 1 (post-injection) and on Week 24. The form captured responses of “Study drug injection,” “Injection of 2 mL inactive vehicle substance,” “Needle insertion into the knee with no vehicle substance injected” and “Do not know”.

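### The blinding index in SAP 7.5.3 uses a two-choice formula on three possible guesses, so zero does not mean random guessing

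*SAP*

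**What the plan says.** Subjects report "which treatment arm of the study they believe they were assigned to in order to evaluate the effectiveness of blinding" (Protocol 7.1.1), on Day 1 after the injection and at Week 24. The form has three definite answers and *Do not know*. Vehicle ("Injection of 2 mL inactive vehicle substance", SAP 5.2.8) and sham are separate answers.

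Protocol 10.4.7 plans only that "the percentage of subjects accurately identifying the assigned treatment group will be estimated". On the method, Protocol 10.6.2 says: "Details of this analysis will be provided in the SAP".

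SAP 7.5.3 supplies that method. It cross-tabulates assignment (SM04690 pooled, vehicle, sham) against the four answers and prints the conditional probability in each cell. For each row it then computes Bang's index: twice the correct share among all definite guesses, minus 1, multiplied by the share who gave a definite guess. The index "will be calculated to determine the percentage of unblinding that is beyond chance". According to the legend, 0 "represents random guessing", 1 is complete unblinding and −1 is opposite guessing.

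**The concern.** The factor 2p − 1 is zero at p = 1/2, which is the chance of a correct guess between two options. The SAP's denominator contains three. Neither document merges vehicle with sham for this index, restricts the denominator to two answers, or states a chance probability, so the zero point does not fit the table it is applied to.

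A reader who follows the legend can go wrong in two ways. A fully blinded result gives negative values, which lean towards the opposite-guessing end of the scale. A value of 0, read as random guessing, can conceal real unblinding. The sham row matters most. Protocol 6.1.5 takes deliberate steps to conceal the sham procedure, and SAP 7.5.4 compares vehicle with sham on patient-reported outcomes. Readers of that comparison will want to know whether sham subjects could tell.

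**Working it through.** **Inputs.** The formula and legend come from SAP 7.5.3, and the answer options from Protocol 7.1.1 and SAP 5.2.8. For allocation, Protocol 10.5 states: "A sample size of approximately 630 subjects will be randomized at a ratio of 1:1:1:1:1:1". That gives 630/6 = 105 per arm and 4 × 105 = 420 in the pooled active row. The documents give no *Do not know* share (DK) and no guessing pattern, so both are assumed below.

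**1. What the index is.** Let c be the correct guesses, g the definite guesses and N the row total:

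(2c/g − 1) × (g/N) = (c − (g − c))/N = P(correct) − P(incorrect) = (2p − 1)(1 − DK), with p = c/g.

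**2. The SAP's anchors.** With DK = 0, p = 1 gives +1 and p = 0 gives −1, so both end anchors reproduce. Zero requires p = 1/2. Three equally likely answers give p = 1/3 and an index of −(1 − DK)/3, so the zero anchor does not reproduce.

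**3. Any fully blinded pattern.** Full blinding means the same shares q1 + q2 + q3 = 1 among guessers, and the same DK, in every arm. The three indices then sum to

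(2(q1 + q2 + q3) − 3)(1 − DK) = −(1 − DK).

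Three zeros would need q1 = q2 = q3 = 1/2, which adds to 1.5. At least one index must be −(1 − DK)/3 or lower.

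**4. Size under full blinding.**

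| Guessing pattern, same in all arms (drug/vehicle/sham) | Row | DK 0% | DK 20% | DK 50% |
|---|---|---|---|---|
| Equal | each | −0.33 | −0.27 | −0.17 |
| 25/25/50 | active, vehicle | −0.50 | −0.40 | −0.25 |
| 25/25/50 | sham | 0.00 | 0.00 | 0.00 |
| Sum of the three rows, either pattern | | −1.0 | −0.8 | −0.5 |

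Sampling error does not usually hide the shift. With equal guessing and DK 25%, the index is −0.25. Its expected 95% interval is −0.33 to −0.17 for 420 subjects and −0.41 to −0.09 for 105. Only at a very high DK does the interval for a 105-subject row reach zero (at 75%: −0.18 to 0.01).

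**5. One index value, different facts.** Take DK 20%, with 42 of 105 sham subjects naming sham. The sham index is (2 × 42/84 − 1) × 84/105 = 0. The meaning depends on how many vehicle subjects also name sham:

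| Vehicle subjects naming sham | Sham minus vehicle | Wald 95% CI |
|---|---|---|
| 42/105 | 0.40 − 0.40 = 0.00 | −0.13 to 0.13 |
| 28/105 | 0.40 − 0.27 = 0.13 | 0.01 to 0.26 |
| 21/105 | 0.40 − 0.20 = 0.20 | 0.08 to 0.32 |

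**6. Would a three-choice rescaling suffice?** The factor (3p − 1)/2 × (1 − DK) is zero under equal guessing. It moves away from zero under other blinded patterns. If all arms guessed 4:1:1 (hypothetical, matching the 420:105:105 rows) with DK 0, the active row reads (3 × 2/3 − 1)/2 = +0.50, against +0.33 for the SAP index. At 25/25/50 the sham row reads +0.25, against 0. Its minimum is −0.5, so the −1 label would also have to change.

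**The case against.** The strongest reply is that almost nothing depends on this. Subject perception is exploratory in both documents, and the SAP attaches no test, interval or threshold to the index. No analysis or decision uses it. The conditional cell probabilities are printed for Day 1 and Week 24, so a reader can see the guessing pattern and subtract cells unaided. All of that stands and limits the severity.

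Narrower points also have some force:

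- If everyone answers *Do not know*, the sum −(1 − DK) is 0. The printed formula is then 0/0, so this is a degenerate exception.
- The legend labels only −1 as opposite guessing. Values from −0.17 to −0.50 lie between its anchors and can be read as partly opposite at most.
- No single-row index can separate a preference for one answer from unblinding, even with two choices. The example in step 5 illustrates that general limit and is not itself proof of the factor-of-two error, which rests on steps 2 and 3.
- Neither document promises an interval, so adding one is an improvement and its absence contradicts nothing.
- At Week 24, guesses may reflect perceived benefit. A between-arm contrast cannot distinguish that from a failure of the injection procedure, and neither can any other blinding summary.

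None of these makes 0 the value under random guessing for the table as planned.

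**Conclusion.** The concern holds and is minor. The zero anchor and the beyond-chance description are wrong for a table with three definite guesses; the anchors +1 and −1 are right. Under equal guessing every row is displaced to −(1 − DK)/3. Under any guessing pattern shared by all arms, the three rows sum to −(1 − DK). These two results are algebraic and depend only on the printed formula. The numerical sizes depend on the assumed DK shares and guessing patterns. The conclusion does not rely on the paper cited for the index. The harm is confined to misreading an exploratory blinding summary.

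**What to change.** 1. In SAP 7.5.3, remove or correct the statements that 0 is random guessing and that the index measures unblinding beyond chance. State that the index is P(correct) minus P(incorrect), with value −(1 − DK)/3 under equal-probability three-choice guessing.
2. As the chance-corrected summary, report P(guess i | assigned i) minus P(guess i | assigned to another arm), with 95% intervals, at Day 1 and Week 24. Name the contrasts in advance, for example naming sham in sham versus vehicle and naming study drug in active versus vehicle. Without unblinding the expected value is 0 whatever the shared guessing pattern. Add that Week 24 guesses may also reflect perceived benefit.
3. Treat the three-choice rescaling as optional, and use it only with its equal-probability assumption stated and its lower anchor given as −0.5.

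The cost is one changed interpretation line and a few subtractions of cells already in the planned table. The contrasts are only moderately precise. With no unblinding, DK 20% and all 630 subjects answering, the 95% half-width is 0.09 to 0.13 for sham versus vehicle and 0.09 to 0.11 for active versus vehicle, over the equal, 25/25/50 and 4:1:1 patterns. Missing Week 24 forms would widen these.

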7.5.4. Comparison of Vehicle and Sham

The change from baseline in weekly Pain NRS, WOMAC Pain, WOMAC Function and PTGA at Weeks 4, 8, 12, 16, 20 and 24, as well as mJSW at Week 24 will be analyzed with an ANCOVA model with the following hypothesis:

$$H_0: (\beta_{\text{vehicle}} - \beta_{\text{sham}}) = 0 ; H_A: (\beta_{\text{vehicle}} - \beta_{\text{sham}}) \neq 0$$

Least squares estimate of difference between vehicle and sham in the change in outcome from baseline, adjusted for baseline value, will be reported along with unadjusted 95% confidence intervals and P values.

7.5.5. Subgroup Analysis

Efficacy analyses described in Sections 7.3 and 7.4 will be further analyzed by additional, complementary clinical phenotypes of OA not already defined in Section 7.1.

The additional clinical phenotypes of OA include:

1. Bilateral Symptomatic OA
2. $WPI \leq 4$ and $SSQ2 \leq 2$
3. $WPI > 4$ and/or $SSQ2 > 2$
4. Unilateral Symptomatic OA with $WPI > 4$ and/or $SSQ2 > 2$
5. Bilateral Symptomatic OA with $WPI \leq 4$ and $SSQ2 \leq 2$

6. Bilateral Symptomatic OA with WPI > 4 and/or SSQ2 > 2

7.5.6. Concordance Analysis

Logistic regression will be conducted within each treatment group to determine whether baseline-adjusted change in mJSW is concordant with response criteria for Pain NRS, WOMAC Pain, WOMAC Function, and Patient Global. Response criteria will be patterned after the OMERACT-OARSI response criteria (Pham 2003); a responder must have a 50% improvement with corresponding 20 point (out of 100) actual scale improvement. Each outcome will be modeled individually, and OMERACT-OARSI ‘strict’ responder (response on either WOMAC Pain or WOMAC Function) as well as Pain and Function responder (response on both WOMAC Pain and WOMAC Function) will also be modeled. Receiver operator characteristic (ROC) curves and ROC areas under the curve (AUC) will be provided.

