7.2. ANCOVA Model for Continuous Efficacy Outcomes

ANCOVA models will be used for all continuous efficacy outcome measures summarized by change from baseline in order to test the following four hypotheses:

$$H_0: (\beta_i - \beta_0) = 0$$

$$H_A: (\beta_i - \beta_0) \neq 0, \text{ where } i = 1,2,3,4$$

In the statement above, β is the least squares estimate in the change in the continuous efficacy outcome from baseline at each timepoint (where β_0 is the estimate for vehicle), and i represents each of the four SM04690 treatment groups.

Least squares estimate of difference between each treatment group and placebo in the change in the continuous efficacy outcome from baseline at each timepoint, adjusted for baseline value, will be reported along with unadjusted 95% confidence intervals and P values.

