7.3. Analysis of Primary Efficacy Endpoints

The change from baseline in weekly Pain NRS, WOMAC Pain, WOMAC Function and mJSW at Week 24 will be analyzed with the ANCOVA model described in Section 7.2. Figures displaying the change in outcome over time will be provided for the FAS and mFAS.

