7.4. Analysis of Secondary Efficacy Endpoints

The change from baseline in PTGA at Week 24 will be analyzed with the ANCOVA model described in Section 7.2. Figures displaying the change in PTGA over time will be provided for the FAS and mFAS.

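### The concordance analysis in SAP 7.5.6 relates mJSW change to symptoms only through responder yes/no outcomes; a continuous analysis should be added beside it

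*SAP*

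**What the plan says.** SAP 7.5.6 states: "Logistic regression will be conducted within each treatment group to determine whether baseline-adjusted change in mJSW is concordant with response criteria". The scores are Pain NRS, WOMAC Pain, WOMAC Function and Patient Global. Response is defined as follows: "a responder must have a 50% improvement with corresponding 20 point (out of 100) actual scale improvement". The two composites are binary as well: "Each outcome will be modeled individually, and OMERACT-OARSI ‘strict’ responder (response on either WOMAC Pain or WOMAC Function"; the other requires response on both WOMAC subscores. ROC curves and their areas accompany the models.

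The same variables are continuous elsewhere in the SAP. Section 7.2 says "ANCOVA models will be used for all continuous efficacy outcome measures summarized by change from baseline". Section 7.3 adds "The change from baseline in weekly Pain NRS, WOMAC Pain, WOMAC Function and mJSW at Week 24 will be analyzed with the ANCOVA model", and Section 7.4 adds "The change from baseline in PTGA at Week 24 will be analyzed with the ANCOVA model described in Section 7.2". No section regresses a symptom change on mJSW change or correlates the two.

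Section 7.5.6 sits under the exploratory analyses and sets no alpha, power or decision rule. SAP 7.6 bases dose selection on the Week 24 ANCOVA results, not on 7.5.6.

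**The concern.** mJSW, Pain NRS, WOMAC Pain and WOMAC Function are the four primary endpoints, and 7.5.6 is the one planned look at whether structure and symptoms move together. On the responder scale, a subject who improves by 48% counts the same as one who worsens, and one who improves by 52% the same as one who improves by 95%. The models are also fitted one arm at a time. A modest true association is then estimated imprecisely, and a null responder model could be read as evidence that joint space gain does not go with clinical benefit. The SAP names published criteria as the pattern for the cut, but gives no reason to study the association on that scale alone.

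**Working it through.** There is no planned figure to reproduce: the documents state no power, correlation or responder rate for this analysis.

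**Inputs from the documents**
- Total size and allocation, Protocol 10.5: "A sample size of approximately 630 subjects will be randomized at a ratio of 1:1:1:1:1:1". Per arm: 630/6 = 105. (SAP 3.1 prints one fewer 1 in the ratio but lists six arms; six is used.)
- Population shares, SAP 3.2: 50% unilateral, 80% without widespread pain. Unilateral: 105 × 0.5 = 52.5, about 53 per arm. Unilateral without widespread pain: 52.5 × 0.8 = 42 per arm. SAP 7.1 repeats all efficacy analyses in these populations.
- Missing data are not imputed (SAP 9.4) and no dropout rate is given. A 20% loss, assumed, gives 105 × 0.8 = 84.

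**Assumptions, not in the documents**
- Correlation r between baseline-adjusted mJSW change and symptom change: 0.1 to 0.3.
- Responder rate p: 20% to 60%.
- Two-sided 5% test, to match the 95% intervals used elsewhere.

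**Step 1: information kept.** For a normal outcome cut at responder rate p, the fraction kept for a modest association is φ(z_p)² / [p(1 − p)].
- p = 0.2: 0.280² / 0.16 = 0.49
- p = 0.3: 0.348² / 0.21 = 0.58
- p = 0.5: 0.399² / 0.25 = 0.64
- p = 0.6: 0.386² / 0.24 = 0.62

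The inverse, 1/0.64 to 1/0.49, is about 1.6 to 2.0 times as many subjects for the same precision. Standard errors are about 1.25 to 1.4 times larger.

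**Step 2: power on the continuous scale.** Fisher z: power ≈ Φ(atanh(r)·√(n − 3) − 1.96).
- n = 105, r = 0.2: 0.2027 × 10.10 − 1.96 = 0.09, so 54%
- n = 105, r = 0.3: 0.3095 × 10.10 − 1.96 = 1.17, so 88%

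**Step 3: simulated power, cut against continuous.** Likelihood-ratio test in the logistic model against the linear regression test, 6,000 runs per cell, over the four responder rates in Step 1.

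| n per arm | r = 0.1 | r = 0.2 | r = 0.3 |
|---|---|---|---|
| 105 | 12-14% vs 18% | 31-37% vs 54% | 59-71% vs 88% |
| 84 | 11-12% vs 15% | 25-32% vs 45% | 50-60% vs 80% |
| 53 | 9% vs 11% | 18-23% vs 31% | 34-44% vs 60% |
| 42 | 8% vs 9% | 16-19% vs 25% | 29-36% vs 49% |

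**Step 4: the SAP's own rule.** Applied to baselines of 40-80 on a 0-100 scale, with assumed change SD 22 and mean improvement 15-30 (responder rate 25-50%):
- n = 105: 33-38% vs 52-53% at r = 0.2; 64-72% vs 87-88% at r = 0.3
- n = 53: 19-23% vs 29% at r = 0.2; 38-44% vs 58-59% at r = 0.3
- n = 42: 18-19% vs 23-24% at r = 0.2; 31-35% vs 48% at r = 0.3

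The 20-point condition never bound in this range, since half of 40 is already 20.

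**Step 5: a different shape.** Suppose instead that subjects fall into two classes with mean changes −42 and −10, and that class probability is logistic in standardised mJSW change with slope 0.6. Cut against continuous at within-class SD 10, 15 and 22:
- n = 105: 66% vs 66-69%, 48-49% vs 52-56%, 30-31% vs 36-38%
- n = 52: 37-38% vs 37-40%, 26-27% vs 29-31%, 17-18% vs 20-21%

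The gain falls to about 0-7 points, but the continuous model does no worse than the cut.

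**The case against.** The strongest reply is that the binary form is the question asked. Section 7.5.6 asks about concordance with response criteria, and ROC curves and responder composites need a binary outcome. A slope answers a different question and has no counterpart for the composites. This stands, and it rules out demoting the responder models.

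The gain also depends on shape. Bivariate normality with a linear link favours linear regression, and Step 5 shows how little is left under a mixture. This stands too.

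Third, the fix does not cure small arms. With 53 per arm and r = 0.2, the continuous model has about 30% power, so a null result remains likely on either scale.

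Fourth, the section is exploratory and sets no test, and Protocol 10.2 says that no formal hypotheses are tested. That limits the weight of the point. It does not remove it, because the loss of precision in Step 1 applies to interval estimates whether or not a test is run.

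A reader might infer that a true structure-symptom link would be missed far more often under the planned analysis. The documents do not support that as a general statement: it needs a correlation they do not give and a significance test that 7.5.6 does not set. With 105 per arm, the assumed cases give these miss rates, continuous against cut:
- r = 0.1: 82% against 86-88%, nearly equal
- r = 0.2: 46% against 63-69%, about 1.4 to 1.5 times
- r = 0.3: 12% against 29-41%, about 2.5 to 3.5 times

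Only the last comes near that description.

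**Conclusion.** The point holds as a gap in an exploratory section. The only analysis linking mJSW change to symptom change discards about 36-51% of the available information under a normal, roughly linear link, although the continuous changes are already derived.

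Combining the simulations, power with 105 per arm is about 31-38% against 52-54% at r = 0.2, and 59-72% against 86-88% at r = 0.3. The gain is about 4-7 points at r = 0.1. In the unilateral populations (42-53 per arm) it is roughly 4-20 points at r = 0.2-0.3, reaching about 26 only at a 20% responder rate with 53 per arm and r = 0.3. Under a responder mixture it is about 0-7 points.

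All of these rest on assumed correlations, responder rates and change SDs, and mostly on complete data. Neither the primary comparisons nor dose selection is affected. This is a worthwhile, low-priority improvement.

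**What to change.** In SAP 7.5.6, keep the responder logistic and ROC models and add a linear regression within each treatment group. The outcome is the Week 24 change in each symptom score (weekly Pain NRS, WOMAC Pain, WOMAC Function, PTGA). The predictor is the Week 24 change in mJSW, adjusted for baseline symptom score and baseline mJSW. Report the slope or partial correlation with a 95% CI. State that a null responder model alone will not be taken as absence of a structure-symptom link.

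The cost is a short text change and a few more model runs on variables already derived; no new data are needed. The added model assumes approximate linearity, and a slope is less directly clinical than a responder odds ratio. The retained responder models cover that side.
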